#### 1.2.5 Rationale for Timing of Treg Administration

Most animal studies of Treg administration have administered Treg at the time of transplantation, in contrast to our study which proposes to give Tregs approximately 12-20 weeks after liver transplant. There are no published studies to our knowledge that have examined the optimal timing for Treg administration. In addition, modeling such studies in animals is difficult due to the variable responses of animals to conventional IS. In addition, the administration of T cell depleting agents often results in long term graft acceptance without further manipulation. Liver transplantation in particular is difficult to model due to the natural tolerogenicity of liver allografts which often require no IS for long-term survival.

We have chosen to delay Treg administration for several reasons. First, in the setting of liver transplantation, the potential for complications is very high, especially early after transplantation. In the context of a safety trial, administering Tregs at the time of transplant would be prohibitively risky. In addition, we expect that the window of T cell depletion after Thymoglobulin® will last at least until the time of Treg administration, 11-20 weeks after liver transplant. Thymoglobulin induction in renal transplant patients induced CD4 depletion out to at least 28 weeks, with no increase in CD4 counts between weeks 12-28 (Tang Q. J., 2012)(See Figure 1). This timing will also allow us to transition eligible subjects to an mTOR-based regimen, which is difficult immediately after liver transplantation for reasons discussed in *Section 1.2.2*. Waiting 11-20 weeks is also beneficial to a safety trial because the incidence of rejection is expected to be lower at that

Confidential Page 22 of 80

time point, allowing a cleaner evaluation of the safety of Treg administration. Delayed administration will also enable us to manufacture darTregs as donor cells are required.

**Figure 1.** Repopulation of CD4+ T cells after Thymoglobuin induction in renal transplant patients. X axis denotes weeks after transplant and Y axis represents Total cell number/ml blood (x  $10^6$ ). Open circles, control arm. Filled circles, thymoglobulin induction arm.

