#### 3. Study Design

#### 3.1 Description of Study Design

This is a multi- center, open-label, dose- escalation, pilot study in which adult subjects undergoing primary solitary liver transplant will receive a T cell depletion agent (Thymoglobulin®) followed by Treg-supportive IS regimen based on either EVR or reduced-dose TAC (Cohorts 1a and 1b). Subjects in subsequent cohorts will also receive a single infusion of autologous, darTregs (Cohort 2: 50 million darTregs; Cohort 3: 200 million darTregs: or Cohort 4: 800 million darTregs). For individual participants, there are up to three successive stages in the study with specific eligibility criteria for each stage. As shown in *Figure* 8, the three stages are:

- Screening and Enrollment
- Eligibility assessment for EVR conversion and proceeding to T-reg infusion
- darTreg Infusion

Subjects will be followed for 40 weeks after transplant, during which clinical data along with peripheral blood (PBMCs and serum) and liver biopsy samples will be collected and analyzed (Appendix 1, 2 3).

[figure not shown]

Figure 8. Three Stages of Trial

The four cohorts are summarized below, with details about the dose escalation plan in Section 5.4.

- Cohort 1: 3 subjects from Center 1 (Cohort 1a) + 3 subjects from Center 2 (Cohort 1b); these subjects will undergo T cell depletion followed by TAC- or EVR-based IS (Stage 1 and 2; they will not receive darTreg infusion (Stage 3)).
- Cohort 2: 3 subjects meeting eligibility criteria for all 3 Stages will receive 50 million darTregs (Dose A range 25-60 million).
- Cohort 3: 3 subjects meeting eligibility criteria for all 3 Stages will receive 200 million darTregs (Dose B range 100-240 million).
- Cohort 4: 6 subjects meeting eligibility criteria for all 3 Stages will receive 800 million darTregs (Dose C range 400-960 million).

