### 5.2.3 Thymoglobulin® Study Dosing and Administration

[figure not shown]
For this study, subjects will be given a dose range of 3.0-4.5 mg/kg total. Subjects who meet eligibility criteria for Thymoglobulin® will be given the first dose no later than 72 hours after transplantation. For transplants occurring during overnight hours, the first dose might begin on Day 2.

The first and second doses of Thymoglobulin® must be 0.75 mg/kg administered over 12 hours. Additional doses of 0.75 -1.5 mg/kg IV will be administered over 6-12 hours, or at the site investigator's discretion, until CD3 count is less than or equal to 50 cells/ $\mu$ L (50 cells/mcL) or total lymphocyte count is less than or equal to 0.10 x 10 $^9$ /L when CD3 count is unavailable; or when the maximal dose of 4.5/mg/kg has been given.

Note: If Myfortic is used, dosing should be 360 mg BID.

Figure 9. EVR-based Regimen after Thymoglobulin®

Note: If Myfortic is used, dosing should be 360 mg BID.

Figure 10. TAC-based Regimen after Thymoglobulin®

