# 14.3 Grading and Attribution of Adverse Events

#### 14.3.1 Grading Criteria

The study site will grade the severity of AEs experienced by the study subjects according to the criteria set forth in the NCI-CTCAE — Version 4.0 for all AEs with the exception of Infection. The NCI-CTCAE manual provides a common language to describe levels of severity, to analyze and interpret data, and to articulate the clinical significance of all AEs. The NCI-CTCAE has been reviewed by the study investigators and has been deemed appropriate for the subject population to be studied in this protocol for all AEs with the exception of infection and hematologic events described below.

AEs will be graded on a scale from 1 to 5 according to the following standards in the NCI-CTCAE manual:

- Grade 1 = mild AE.
- Grade 2 = moderate AE.
- Grade 3 = severe and undesirable AE.
- Grade 4 = life-threatening or disabling AE.
- Grade 5 = death.

For any AE of Infection, the following grading system will be used for study participants:

- Grade 1 = asymptomatic; clinical or diagnostic observation only; intervention with oral antibiotic, antifungal, or antiviral agent only; no invasive intervention required
- Grade 2 = symptomatic; intervention with intravenous antibiotic, antifungal, or antiviral agent; invasive intervention may be required
- Grade 3 = any infection associated with hemodynamic compromise requiring pressors; any infection necessitating ICU level of care; any infection necessitating operative intervention; any infection involving the central nervous system; any infection with a positive fungal blood culture; any proven or probable aspergillus infection; any tissue invasive fungal infection; any pneumocystis jiroveci infection
- Grade 4 = life-threatening infection
- Grade 5 = death resulting from infection

Other than those described below, any events grade 2 or higher (including study defined grading of infections) will be recorded on the appropriate AE CRF for this study.

For hematologic events listed below, grade 3 or higher will be recorded on the appropriate AE case report form (CRF) for this study:

- Neutrophil count decreased
- Anemia (Hemoglobin decreased)
- Platelet count decreased
- Total lymphocyte count decreased
- Lymphocyte subset count decreased (including CD4)

Decreased CD4 lymphocytes and lymphocyte counts within 6 months after last study dose of Thymoglobulin® do not require reporting.

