PBMC Collection Visit does not apply to Cohort 1. Cohort 2 can have whole blood collection for PBMC isolation if hemoglobin is ≥10.5 mg/dl; leukapheresis if <10.5 mg/dl.

<sup>2 Screening for eligibility C1 and C2 can be assessed between 5-6 weeks (30-44 days) after transplantation. Everolimus can be started on or after 30 days after liver transplantation if eligibility criteria are met (Screen C1).

 $^3\mbox{HIV/HBV/HCV}$  serology can be within one year of screening.

<sup>4AFP is only required for subjects known to have HCC. At Screen A, AFP should be drawn if unavailable within 3 preceding months; AFP should be redrawn at time of transplant. After transplant, AFP should be recorded every 3 months.

<sup>5 First EVR level should be obtained within one week of first dose (+/- 2 days). MMF discontinuation and TAC trough 3-5 μg/L for subjects converting to EVR only. Subjects continuing on TAC-based IS should have troughs 6-8 μg/L.

<sup>6 Prior to Thymoglobulin, collect AE's/SAE's occurring within 72 hours after PBMC Collection only. Collect all AE's/SAE's grade 2 and higher from the time of first Thymoglobulin infusion.

<sup>7 Central laboratory assessments may be drawn up to one year BEFORE solumedrol dose in OR. Once drawn, mechanistic labs do not need to be repeated.

<sup>8CBC, Basic Chemistry, Liver Function Tests, and PT/INR/PTT should be collected as close to, but prior to transplant as possible.

<sup>9Liver allograft biopsy should be obtained prior to transplantation (back table) for local pathology reading only, no specimen for central pathology

<sup>10 Screening should take place within 24 hours prior to Thymoglobulin®. The first dose of Thymoglobulin® is to be given within 72 hours after transplantation. Additional doses of 0.75-1.5 mg/kg IV will be administered until CD3 count is ≤50 cells/μL (50 cells/mcL) or total lymphocyte count is ≤ 0.10 x 10 ½L; or when maximum dose of 4.5/mg/kg has been given. Day 2 and Day 6 visits are only needed if Thymoglobulin is given on these days.

 Treg expansion should be initiated 2-3 weeks prior to planned Treg infusion if subjects continue to meet eligibility criteria. Please refer to Stage 3 Schedule of Events. .

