9.2 Adverse Events

All adverse events will be classified by system organ class and preferred term, according to a standardized thesaurus (MedDRA version 17.0). The severity of AEs will be classified using the National Cancer Institute's Common Toxicity Criteria for Adverse Events, with the exception of infections which will be graded according to protocol definitions.

An overall summary table will be developed to report the number of events and the number and percentage of subjects having at least one event in the following categories:

- AEs
- AEs indicated as serious (SAEs)
- AEs that lead to study discontinuation
- AEs with an outcome of death
- AEs reported by maximum severity

In addition, adverse events classified by MedDRA system organ class and preferred term will be summarized for each study cohort and overall for each of the following:

- All AEs
- AEs by maximum severity
- AEs by study stage

The summary tables will present the total number of events as well as the number and percentage of subjects experiencing the events. When reporting the number of AEs, if the same AE occurs for a subject on multiple occasions the event will be counted once for each occurrence. When reporting the number of subjects experiencing the events, a subject will only be counted once if they ever experience an event within the particular system organ class or preferred term. Percentages will be based on the number of subjects in the analysis population.

A summary table of incidence rates adverse events classified by system organ class and MedDRA preferred term will be provided. Incidence rate for a system organ class or preferred term will be defined as the number of adverse events divided by the person-time since the subject enrolled.

Separate data listings will be provided for AEs leading to study discontinuation.

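### Decreased lymphocyte and CD4 counts must be reported for only about a third of follow-up, and in infused subjects only in Stage 3, yet SAP 9.2 analyses them over all enrolled time and by stage

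*Protocol*

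**What the plan says.** Protocol 14.3.1 lists the blood-count events to be recorded as AEs at Grade 3 or higher. The list includes decreased total lymphocyte count and "Lymphocyte subset count decreased (including CD4"). The same section then removes the duty to report for a period: "Decreased CD4 lymphocytes and lymphocyte counts within 6 months after last study dose of" Thymoglobulin do not have to be reported.

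SAP 9.2 makes no exception for these terms. The incidence rate for each system organ class and preferred term is "defined as the number of adverse events divided by the person-time since the subject enrolled". The same section plans system organ class and preferred term summaries, for each cohort and overall, that include "AEs by study stage". Neither part of SAP 9.2 mentions the exempt period.

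On timing, Protocol 3.1 states that "Subjects will be followed for 40 weeks after transplant". Protocol 10.4 places infusion at weeks 11 to 20, and Protocol 5.1.3 makes week 20 the latest date. Protocol 14.8.1 starts Stage 3 at the first receipt of any darTregs.

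**The concern.** A rate needs a numerator and denominator that cover the same time. Here the denominator runs from enrolment to the end of follow-up, while sites are required to supply cases only for the last part of it. The printed rate then describes no defined period.

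The by-stage table has a related fault. In Cohorts 2 to 4, Stage 2 after the last Thymoglobulin dose lies wholly inside the exempt period. The regimen aims to deplete T cells (dosing under Protocol 5.2.3 continues until CD3 is at or below 50 cells/µL or the maximum dose is reached), yet required lymphopenia reports in that part of Stage 2 are zero by rule. Any that appear must stand in Stage 3. A reader of the table could take this as a change at infusion. Over-immunosuppression is a named darTreg risk in Protocol 9.3.2, so the reading matters. Protocol 1.2.5 also cites renal transplant data in which Thymoglobulin "induced CD4 depletion out to at least 28 weeks, with no increase in CD4 counts between weeks 12-28", so depletion could outlast the exemption. The protocol does not say whether a persisting low count then becomes reportable, or with what onset date.

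**Working it through.** **1. The plan's own figures.** Protocol 15.6 gives 18 × 12 = 216, 12 × 28 = 336 and 6 × 40 + 12 × 12 = 384 person-weeks. The two analysis periods sum to 384 + 336 = 720 = 18 × 40. The limits in Protocol Table 8 reproduce as exact Poisson limits, for example 2 events in 216 person-weeks: 0.0093 (0.0011 to 0.0334). The documents state no rate for lymphopenia or low CD4.

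**2. Inputs.**
- Follow-up: 40 weeks after transplant (Protocol 3.1).
- First Thymoglobulin dose: eligible subjects "will be given the first dose no later than 72 hours after transplantation" (Protocol 5.2.3).
- Dosing days: the schedule runs from day 2 to day 6, since "Day 2 and Day 6 visits are only needed if Thymoglobulin is given on these days" (Protocol Appendix 1).
- Last dose: day 5 is my assumption, with days 2 to 8 as the range.
- Six months: 182 to 182.6 days.

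**3. Reportable share.** The exemption ends at week (day of last dose + 182.6)/7.
- Day 5: 187.6/7 = 26.8, leaving 40 − 26.8 = 13.2 weeks, and 13.2/40 = 33%.
- Day 2 (with 182 days): 184/7 = 26.3, leaving 13.7 weeks, or 34%.
- Day 8: 190.6/7 = 27.2, leaving 12.8 weeks, or 32%.
- Enrolled time before transplant lowers the share. With 26 weeks of it (assumed), 13.2/(40 + 26) = 20%.
- Protocol 10.4 also speaks of 28 weeks after infusion. For an infusion at week 20 that would run to week 48, and the share would be (48 − 26.8)/48 = 44%. I keep to the 40 weeks of Protocol 3.1.

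**4. Effect on the listed rate.** With all 18 subjects followed for 40 weeks and no waiting time, E events are divided by 720 instead of 18 × 13.2 = 237.6. The factor is 720/237.6 = 3.0. As an illustration, take 4 events, whose exact Poisson limits are 1.090 and 10.242 events:
- over 720 person-weeks: 0.0056 per week (0.0015 to 0.0142);
- over 237.6 person-weeks: 0.0168 per week (0.0046 to 0.0431).

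**5. Relation to the true 40-week rate.** Let r be the event rate in the exempt weeks divided by the rate afterwards. Then listed/true = 13.2/(13.2 + 26.8r):
- r = 0.5: 0.50
- r = 1: 0.33
- r = 2: 0.20
- r = 5: 0.09
- r = 10: 0.05

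The documents do not give r.

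**6. By stage.** The earliest end of the exemption is week 26.3 and the latest infusion is week 20, a gap of at least 6.3 weeks. So for every infused subject, all Stage 2 time after the last dose is exempt, and so are at least the first 6 weeks after infusion. Cohort 1 stays in Stage 2 throughout. In planned person-weeks:
- Stage 2: 6 × 13.2 = 79.2 of 384 reportable (21%), all from Cohort 1.
- Stage 3: 12 × 13.2 = 158.4 of 336 reportable (47%).
- Stage 3 share of reportable time: 158.4/237.6 = two thirds.

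**The case against.** The exemption is sensible in itself: it keeps the intended effect of a depleting agent out of the AE log. The analysis is descriptive. The selected safety outcomes (Protocol 3.2, SAP 8.1.1) name anaemia, neutropenia and thrombocytopenia but not lymphocytes, and the stopping rules in Protocol 14.8.1 do not use these terms. The tables are shown by cohort, and the exemption ends at about the same post-transplant week in all cohorts, so Cohort 1 shows late lymphopenia without darTregs. SAP 9.4 also lists haematology results with out-of-range flags and plots selected tests. All of this stands, and it limits the point to the general AE tables. It does not repair the denominator or the forced zero within Cohorts 2 to 4, and SAP 9.4 plans no lymphocyte or CD4 summary by stage.

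Four stronger readings are tempting, and the documents do not support them:
- **That the listed rate is one third of the true rate.** This needs a constant event rate (step 5). Only the reportable share is fixed by arithmetic.
- **That every case falls in the darTreg stage.** Cohort 1 and subjects treated with Thymoglobulin but never infused remain in Stage 2. The wording is also permissive, so sites may report exempt cases; SAEs are reported regardless (Protocol 14.5.1); and read literally the waiver does not cover the days between first and last dose.
- **That the plan yields an inflated Stage 3 to Stage 2 rate ratio.** The by-stage table gives counts and percentages, and the rate table is not split by stage.
- **That carry-over will appear as new Grade 3 events when the exemption ends.** The renal data show depletion, not its grade. Protocol 1.2.2 expects partial recovery by one month. Protocol 14.3.1 ties a treatment-emergent laboratory AE to an increase in grade.

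**Conclusion.** The point holds for the general AE tables in SAP 9.2. Decreased lymphocyte and CD4 counts must be reported for about 13 of 40 post-transplant weeks (33%; 32-34% for a last dose on days 2 to 8), and for a smaller share of enrolled time if the wait for transplant counts. Restricting to reportable time raises the listed rate about threefold, assuming all counted cases come from that window and follow-up ends at week 40. The size of the bias against the true 40-week rate cannot be stated, because the early rate is unknown. For infused subjects the forced zero in Stage 2 after the last dose needs no assumption about rates: it follows from the dates, with at least 6 weeks to spare. The matter deserves correction before the tables are programmed. It does not bear on the stopping rules or the selected safety outcomes.

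**What to change.** In SAP 9.2, for lymphocyte-count and lymphocyte-subset terms:
- count events and person-time only from 6 months after each subject's last Thymoglobulin dose;
- list separately any case reported before that date, including SAEs, so that none is lost;
- remove these terms from the by-stage table, or footnote them as not required to be reported before that date.

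Moving the start of the person-time clock to transplant or first Thymoglobulin would not be enough, because the exempt weeks would stay in the denominator.

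Describe depletion by stage from laboratory values. For Cohorts 2 to 4, give CD4 as value and change from the infusion-day (T0) value; Protocol Appendix 3 has it at T0, 24 hours, day 7, day 28, and weeks 12 and 28 after infusion. Set this beside Cohort 1 CD4 at weeks 12, 24 and 40 (Protocol Appendix 2). Use lymphocyte counts from CBC differentials only where they are scheduled: Appendix 2, as it reads in the available text, marks CBC for Cohort 1 only at clinically indicated biopsies, so the comparison with Cohort 1 should rest on CD4.

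The cost is SAP wording and a little programming, with no new data. These terms will have fewer person-weeks and so, where an interval is given, a wider one.

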#### 14.3.2 Attribution Definitions

The relationship, or attribution, of an AE to the study therapy regimen or study procedure(s) will initially be determined by the site investigator and recorded on the appropriate AE / SAE form. Final determination of attribution for safety reporting will be determined by DAIT/NIAID. The relationship of an AE to study therapy regimen or procedures will be determined using the descriptors and definitions provided in Table 5. Attribution of Adverse Events. For additional

Confidential Page 58 of 80

information and a printable version of the NCI-CTCAE manual, consult the NCI-CTCAE web site: http://ctep.cancer.gov/reporting/ctc.html.

Table 6. Attribution of Adverse Events

Code	Descriptor	Relationship (to primary investigational product and/or other concurrent mandated study therapy or study procedure)
		Unrelated Category
1	Unrelated	The AE is clearly not related.
		Related Categories
2	Possible	The AE has a reasonable possibility to be related; there is evidence to suggest a causal relationship.
3	Definite	The AE is clearly related.

Attribution assessment for the following study drugs and procedures will be made when a SAE is reported:

- Lymphocyte depletion with Thymoglobulin°
- Treg-supportive IS regimen reduced dose tacrolimus, reduced dose MMF, reduced dose methylprednisolone, and EVR (if applicable)
- darTreg
- PBMC collection (Leukapheresis or 450-500 ml blood draw)
- Liver biopsy

Other than 450-500 ml blood draw for PBMC collection, AEs associated with blood draws do not have to be reported unless the investigator deems an event reportable.

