Study Termination	Subjects who complete the study, are lost to follow up, withdraw consent, or die during the study. Data and specimens will no longer be expected from subjects who are terminated from the study.			
Study Therapy	The investigational agents (darTregs and Thymoglobulin®) and all protocol required medications.			
Withdrawal from Therapy	Subject who stops study therapy prior to protocol described duration.			

Confidential Page 18 of 80

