#### 3.2 Safety Outcomes

The safety, tolerability, and ties of darTreg therapy given within the context of either a TAC- or EVR-based IS regimen will be evaluated with the rate of the following events within 40 weeks of transplantation:

Clinical outcomes that will be described are:

- 1. Incidence and severity of biopsy-proven AR and/or CR (Demetris A. J., 1997) (Demetris A. D., 2000)
- 2. Incidence of ≥ Grade 3 infections as defined in Section 14.3.1
- 3. Incidence of wound complications (≥ CTCAE Grade 3)

Confidential Page 30 of 80

- 4. Incidence of anemia, neutropenia, and/or thrombocytopenia (according to study defined reporting requirements, *Section 14.3.1*)
- 5. Incidence of AEs attributable to the darTreg infusion including infusion reaction / cytokine release syndrome (CRS) (≥ CTCAE Grade 3), and malignant cellular transformation.

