8.1.1 Safety Outcome Analyses

The safety outcomes will be considered in two ways: the absolute number and the person-week incidence rates (*Section 3.2*) of selected adverse events following transplantation. The person-week incidence rate will be estimated using proportions and exact binomial two-sided 95% confidence intervals for the Safety Sample as a whole and within the two analysis periods defined above. The absolute number and the estimated incidence proportions of the following will be reported:

- Biopsy-proven acute and/or chronic rejection
- Grade ≥ 3 infections as defined in Section 13.3.1 of the Protocol
- Wound complications (\geq CTCAE Grade 3)
- Anemia, neutropenia, and/or thrombocytopenia (\geq CTCAE Grade 3)
- Adverse events attributable to the darTreg infusion including infusion reaction/cytokine releaser syndrome (\geq CTCAE Grade 3), and malignant cellular transformation.

Descriptive statistics will also be presented for:

- The severity of biopsy-proven acute and/or chronic rejection
- Reasons for termination of subjects who did not receive leukapheresis
- Use of concomitant medications

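### darTreg-specific attribution is specified only for SAEs, so safety outcome 5 has no stated source for most non-serious darTreg-attributable AEs

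*Protocol*

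**What the plan says.** Protocol 3.2 lists as its fifth safety outcome: "Incidence of AEs attributable to the darTreg infusion including infusion reaction / cytokine release syndrome (CRS") at CTCAE Grade 3 or higher, together with malignant cellular transformation. SAP 8.1.1 carries the same outcome, promises its absolute number and estimated incidence, and words it as "Adverse events attributable to the darTreg infusion including infusion reaction/cytokine releaser syndrome". Both texts say AEs, not SAEs. Both name the two conditions as inclusions, not as the full content of the outcome.

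Protocol 14.3.2 describes attribution in two layers.

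- **All AEs.** "The relationship, or attribution, of an AE to the study therapy regimen or study procedure(s) will initially be determined by the site investigator", and the result is "recorded on the appropriate AE / SAE form". The codes are unrelated, possible and definite. The heading of the attribution table reads "Relationship (to primary investigational product and/or other concurrent mandated study therapy or study procedure").
- **SAEs.** "Attribution assessment for the following study drugs and procedures will be made when a SAE is reported". Five items follow: Thymoglobulin, the Treg-supportive IS regimen, darTreg, PBMC collection and liver biopsy.

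The Study Definitions Page defines study therapy as "The investigational agents (darTregs and Thymoglobulin®) and all protocol required medications". Protocol 14.3.1 sets the recording threshold at Grade 2 for most AEs and Grade 3 for the listed hematologic terms, whether or not the event is serious.

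**The concern.** Outcome 5 is the only listed safety outcome defined by attribution to the investigational cell product, which Protocol 1.4 says had not previously been used in humans. To count it, each event needs a judgement about darTreg in particular. The protocol asks for that judgement only when the event is serious.

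For a non-serious event the specified judgement concerns the regimen or procedures. After infusion a subject is also taking tacrolimus with either everolimus or MMF, and has a protocol liver biopsy one week later (Protocol 8.3). A code of possible at regimen level does not say that darTreg is the suspected cause.

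If the form follows the written rule and no more, the analyst has two poor choices for the open-ended part of the outcome. One is to count only SAEs, which leaves out non-serious product-related events. The other is to count every regimen-related event after infusion, which mixes in effects of the background drugs. Attribution could be assigned later, but the trial is open-label and the judgement would then be made with outcomes known.

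**Working it through.** No stated figure depends on this point, so the main check sets the outcome against the data that the documents specify.

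**Source of each part of outcome 5**

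| Part of outcome 5 | If serious | If not serious |
|---|---|---|
| Infusion reaction or CRS, Grade 3 or higher | darTreg attribution under 14.3.2 | Countable from term, grade and time since the single infusion |
| Malignant cellular transformation | darTreg attribution under 14.3.2 | Very unlikely to arise, given the SAE criteria in 14.2.2 |
| Any other AE attributable to darTreg | darTreg attribution under 14.3.2 | No source specified |

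The last cell is not empty in principle. Protocol 5.4.3 and 9.3.2 name infection through over-immunosuppression and rejection through contaminating effector cells as darTreg risks. Infections are recorded from Grade 2, and background immunosuppression can also cause them.

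**Other provisions that might supply the judgement**

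- Protocol 15.4.1 and SAP 5 assign AEs to the darTreg period by time of infusion. That gives timing, not attribution.
- SAP 8.1.1 does not say which codes make an event attributable or whose assessment is used.
- SAP 9.2 tabulates AEs by seriousness, discontinuation, death, severity, cohort and stage, but not by relationship.

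**How many events could be involved**

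The only relevant counts are those for the earlier polyclonal Treg trial in type 1 diabetes (Protocol 1.4).

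- By grade: 58 + 25 + 8 = 91 AEs (Grades 1, 2 and 3).
- By relationship: 30 possible + 15 unlikely + 46 unrelated = 91.
- SAEs: 3, of which 1 was unlikely related and 2 unrelated. None was possibly related, so all 30 possibly related AEs were non-serious.
- At Grade 2 or higher: 25 + 8 = 33.

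Grade is not cross-tabulated with relationship. Since 30 is less than 58, all 30 possibly related events could have been Grade 1 and so generally not recorded here. Since 30 is less than 33, all 30 could have been Grade 2 or 3. The number meeting this protocol's threshold is therefore between 0 and 30. Any hematologic Grade 2 events among them would lower the upper end.

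**Illustration with assumed counts**

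Protocol Table 8 uses 12 × 28 = 336 person-weeks for the darTreg period. Suppose 6 events were truly attributable to darTreg.

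- All 6 counted: 6/336 = 0.0179 per person-week (95% CI 0.0066 to 0.0389), a row of Table 8.
- Only 2 serious and counted: 2/336 = 0.0060 (0.0007 to 0.0215), also a row of Table 8.
- None serious: 0, with an exact Poisson upper limit of −ln(0.025)/336 = 0.0110.

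The counts 6, 2 and 0 are assumptions. The documents give no expected split of serious and non-serious events.

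**The case against.** The strongest reply is that the protocol does require an attribution for every AE. The table heading names the primary investigational product, and the AE form, which is not among the documents, may hold a separate darTreg field. Protocol 14.2.1.1 also defines a suspected adverse reaction, for any AE, against the Section 5 agents only, which are darTreg and Thymoglobulin, and DAIT/NIAID makes the final attribution for safety reporting. The Stage 3 thresholds in Protocol Table 7 count listed events after infusion without any test of relatedness, and the analysis is descriptive.

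Much of this stands, and it rules out three stronger readings.

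- A reader might infer that outcome 5 cannot be computed for non-serious events. That goes too far, because Grade 3 or higher infusion reaction or CRS can be counted without any attribution.
- A reader might infer that each AE carries a single relationship code. Section 14.3.2 does not say so, and the form cannot be checked.
- A reader might infer from the earlier trial that all 30 possibly related events would have gone without product-level attribution here. The counts do not support that, because 58 of the 91 events were Grade 1.

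No effect on dose escalation or the stopping thresholds is shown either. What the reply does not supply is a written requirement for a darTreg judgement on a non-serious AE. The definition of a suspected adverse reaction covers two agents together and specifies no data field.

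**Conclusion.** The point holds in a limited form. The written plan specifies darTreg-level attribution only for SAEs, while outcome 5 counts AEs. Non-serious events attributable to darTreg, other than Grade 3 or higher infusion reaction or CRS, have no specified source, and the SAP has no rule for deriving the outcome.

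The size is unknown. The earlier trial shows that product-related events can all be non-serious, but it bounds the relevant number only between 0 and 30, and it used a different product in a different population.

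The conclusion rests on two assumptions: that the AE form follows Section 14.3.2 and asks for no more, and that malignant transformation would meet an SAE criterion. If the form already captures darTreg separately for all AEs, the data are safe. The protocol wording and the missing SAP rule would still need correction.

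**What to change.** 1. In Protocol 14.3.2, apply the existing five-item list to every recorded AE with onset on or after darTreg infusion, not only to SAEs. Keep the present recording thresholds: Grade 2 or higher, and Grade 3 or higher for the listed hematologic terms.
2. In SAP 8.1.1, define outcome 5 as AEs coded possible or definite for darTreg, and state whether the site's or DAIT/NIAID's assessment governs.
3. In SAP 9.2, add a table of AEs by relationship to each component.

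The cost is a few extra AE-form fields for about 12 to 18 infused subjects (3 to 6 in Cohort 2, 3 to 6 in Cohort 3 and 6 in Cohort 4). Treatment, visits and sample size do not change. If the form already has these fields, only the wording of 14.3.2 and the SAP needs to change. This is a cheap improvement.
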